16.11.11. Sleep Disorders

HLGT Sleep Disorders and Disturbances

PT	PT Code
Abnormal dreams	10000125
Abnormal sleep-related event	10061613
Advanced sleep phase	10001423
Behavioural induced insufficient sleep syndrome	10081938
Behavioural insomnia of childhood	10072072
Breathing-related sleep disorder	10006344
Cataplexy	10007737
Circadian rhythm sleep disorder	10009191
Confusional arousal	10067494
Delayed sleep phase	10012209
Dyssomnia	10061827
Exploding head syndrome	10080684
Hypersomnia	10020765
Hypersomnia related to another mental condition	10020767
Hypersomnia-bulimia syndrome	10053712

PT	PT Code
Hypnagogic hallucination	10020927
Hypnopompic hallucination	10020928
Hyposomnia	10067530
Initial insomnia	10022035
Insomnia	10022437
Insomnia related to another mental condition	10022443
Irregular sleep phase	10022995
Irregular sleep wake rhythm disorder	10080301
Loss of dreaming	10065085
Middle insomnia	10027590
Narcolepsy	10028713
Nightmare	10029412
Non-24-hour sleep-wake disorder	10078086
Parasomnia	10061910
Paradoxical insomnia	10083337
Periodic limb movement disorder	10064600
Pickwickian syndrome	10035004
Poor quality sleep	10062519
Rapid eye movement sleep behaviour disorder	10077299
Rapid eye movements sleep abnormal	10037841
Shift work disorder	10078088
Sleep apnoea syndrome	10040979
Sleep attacks	10040981
Sleep disorder	10040984
Sleep disorder due to a general medical condition	10063910
Sleep disorder due to general medical condition, hypersomnia type	10040985
Sleep disorder due to general medical condition, insomnia type	10040986
Sleep disorder due to general medical condition, mixed type	10040987
Sleep disorder due to general medical condition, parasomnia type	10040988
Sleep inertia	10067493
Sleep paralysis	10041002
Sleep sex	10067492
Sleep talking	10041009
Sleep terror	10041010
Sleep-related eating disorder	10067315
Somnambulism	10041347
Somnolence	10041349
Somnolence neonatal	10041350
Sopor	10058709
Stupor	10042264

PT	PT Code
Terminal insomnia	10068932
Upper airway resistance syndrome	10063968

HLGT Sleep disturbances (incl subtypes)

PT	PT Code
Abnormal dreams	10000125
Abnormal sleep-related event	10061613
Advanced sleep phase	10001423
Behavioural induced insufficient sleep syndrome	10081938
Behavioural insomnia of childhood	10072072
Breathing-related sleep disorder	10006344
Cataplexy	10007737
Central-alveolar hypoventilation	10007982
Circadian rhythm sleep disorder	10009191
Confusional arousal	10067494
Delayed sleep phase	10012209
Dyssomnia	10061827
Fatal familial insomnia	10072077
Hypersomnia	10020765
Hyposomnia	10067530
Initial insomnia	10022035
Insomnia	10022437
Irregular sleep phase	10022995
Irregular sleep wake rhythm disorder	10080301
Loss of dreaming	10065085
Microsleep	10076954
Middle insomnia	10027590
Narcolepsy	10028713
Non-24-hour sleep-wake disorder	10078086
Periodic limb movement disorder	10064600
Pickwickian syndrome	10035004
Poor quality sleep	10062519
Rapid eye movement sleep behaviour disorder	10077299
Rapid eye movements sleep abnormal	10037841
Shift work disorder	10078088
Sleep apnoea syndrome	10040979
Sleep deficit	10080881
Sleep inertia	10067493
Sleep paralysis	10041002

PT	PT Code
Sleep sex	10067492
Sleep talking	10041009
Sleep terror	10041010
Sleep-related eating disorder	10067315
Somnambulism	10041347
Sudden onset of sleep	10050014
Terminal insomnia	10068932
Upper airway resistance syndrome	10063968
Catathrenia	10085704

16.11.12. Injection Site Reactions (ISR)

ISR data available in the database, i.e. data collected from non-serious ISR AE eCRF form and collected serious adverse events with 'STUDY DRUG INJECTION SITE' included in the AE term.

16.11.13. Seizures and Seizure-like Events

Convulsions (SMQ)

PT	PT Code
1p36 deletion syndrome	10082398
2-Hydroxyglutaric aciduria	10078971
Acquired epileptic aphasia	10052075
Acute encephalitis with refractory, repetitive partial seizures	10076948
Alcoholic seizure	10056347
Alpers disease	10083857
Aspartate-glutamate-transporter deficiency	10079140
Atonic seizures	10003628
Atypical benign partial epilepsy	10056699
Automatism epileptic	10003831
Autonomic seizure	10049612
Baltic myoclonic epilepsy	10054895
Benign familial neonatal convulsions	10067866
Benign rolandic epilepsy	10070530
Biotinidase deficiency	10071434
CEC syndrome	10083749
CDKL5 deficiency disorder	10083005
Change in seizure presentation	10075606
Clonic convulsion	10053398
Congenital bilateral perisylvian syndrome	10082716
Convulsion in childhood	10052391

PT	PT Code
Convulsions local	10010920
Convulsive threshold lowered	10010927
CSWS syndrome	10078827
Deja vu	10012177
Double cortex syndrome	10073490
Dreamy state	10013634
Drug withdrawal convulsions	10013752
Early infantile epileptic encephalopathy with burst-suppression	10071545
Eclampsia	10014129
Epilepsy	10015037
Epilepsy surgery	10079824
Epilepsy with myoclonic-atonic seizures	10081179
Epileptic aura	10015049
Epileptic psychosis	10059232
Faciobrachial dystonic seizure	10084187
Febrile convulsion	10016284
Febrile infection-related epilepsy syndrome	10079438
Focal dyscognitive seizures	10079424
Frontal lobe epilepsy	10049424
Gelastic seizure	10082918
Generalised onset non-motor seizure	10083376
Generalised tonic-clonic seizure	10018100
Glucose transporter type 1 deficiency syndrome	10078727
GM2 gangliosidosis	10083933
Grey matter heterotopia	10082084
Hemimegalencephaly	10078100
Hyperglycaemic seizure	10071394
Hypocalcaemic seizure	10072456
Hypoglycaemic seizure	10048803
Hyponatraemic seizure	10073183
Idiopathic generalised epilepsy	10071081
Infantile spasms	10021750
Jeavons syndrome	10084303
Juvenile myoclonic epilepsy	10071082
Lafora's myoclonic epilepsy	10054030
Lennox-Gastaut syndrome	10048816
Migraine-triggered seizure	10076676
Molybdenum cofactor deficiency	10069687
Multiple subpial transection	10079825

PT	PT Code
Myoclonic epilepsy	10054859
Myoclonic epilepsy and ragged-red fibres	10069825
Neonatal epileptic seizure	10082068
Neonatal seizure	10082067
Partial seizures	10061334
Partial seizures with secondary generalisation	10056209
Petit mal epilepsy	10034759
Polymicrogyria	10073489
Post stroke epilepsy	10076982
Post stroke seizure	10076981
Postictal headache	10052470
Postictal paralysis	10052469
Postictal psychosis	10070669
Postictal state	10048727
Post-traumatic epilepsy	10036312
Schizencephaly	10073487
Seizure	10039906
Seizure anoxic	10039907
Seizure cluster	10071350
Seizure like phenomena	10071048
Severe myoclonic epilepsy of infancy	10073677
Simple partial seizures	10040703
Status epilepticus	10041962
Sudden unexplained death in epilepsy	10063894
Temporal lobe epilepsy	10043209
Tonic clonic movements	10051171
Tonic convulsion	10043994
Tonic posturing	10075125
Topectomy	10073488
Transient epileptic amnesia	10081728
Tuberous sclerosis complex	10080584
Uncinate fits	10045476
Hemiconvulsion-hemiplegia-epilepsy syndrome	10085010
Juvenile absence epilepsy	10085031
Parietal lobe epilepsy	10085326
Epilepsy of infancy with migrating focal seizures	10086114
Photosensitive seizure	10086294
PURA syndrome	10085882
Epilepsia partialis continua	10015034

PTs (Selective)

PT	PT Code
Confusional state	10010305
Loss of consciousness	10024855
Syncope	10042772
Sopor	10058709
Stupor	10042264
Altered state of consciousness	10050093
Depressed level of consciousness	10012373
Consciousness fluctuating	10050093

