16.11. Appendix 11: Identification of Adverse Events of Special Interest (AESI)

The adverse events of special interest are identified based on MedDRA coded values and/or AE data available in the study database. The PT terms and codes below are from MedDRA 24.1. SMQs use narrow terms unless otherwise specified. In case there is a change to the version of MedDRA at time of reporting, the coded values based on the MedDRA version at the time of reporting will be used. Additional events may be added based on the blinded review of AE data collected on study prior to the database freeze.

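### Two preferred terms in the seizure AESI list share one MedDRA code, so at least one printed code is wrong, and selection on the printed codes would leave out events of at least one of the two

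*SAP*

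**What the plan says.** Section 16.11.13 defines the seizure AESI in two parts: the convulsions SMQ, and a short selective list of eight preferred terms, of which "Altered state of consciousness" is one. Three consecutive rows of the selective list read "Altered state of consciousness 10050093", "Depressed level of consciousness 10012373" and "Consciousness fluctuating 10050093".

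The opening paragraph of Appendix 11 (section 16.11) states how the lists are used: "The adverse events of special interest are identified based on MedDRA coded values and/or AE data available in the study database". It gives the dictionary version, "The PT terms and codes below are from MedDRA 24.1", and provides that if the version has changed by the time of reporting, "the coded values based on the MedDRA version at the time of reporting will be used".

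Section 8.2 describes the groupings as those currently planned and leaves the final terms to the safety review team agreements in force at reporting. Table 4 in that section names seizures and seizure-like events as an AESI for cabotegravir. Section 16.15.7 assigns the AESI summaries to Table 3.71 (by AESI category, system organ class and preferred term) and Table 3.72 (characteristics of the events). Both are due at Month 6, Month 12 and end of study.

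**The concern.** A MedDRA code is an identifier. Two differently named preferred terms in one dictionary version cannot both own the same code, so the list contradicts itself.

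Appendix 11 prints names and codes side by side and does not say which governs when they disagree. A programmer who builds the selection from the code column would retrieve only events of the term that really owns 10050093. Events of the other term would drop out of the seizure AESI, and nothing in Tables 3.71 or 3.72 would show it. If neither term owns the code, both would drop out.

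**Working it through.** No sample size, power or error rate is involved. The check is a count of terms against codes, followed by a reading of the rules that could repair the entry.

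**Inputs: the selective list in section 16.11.13, sorted here by code**

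| Code | Preferred term |
|---|---|
| 10010305 | Confusional state |
| 10012373 | Depressed level of consciousness |
| 10024855 | Loss of consciousness |
| 10042264 | Stupor |
| 10042772 | Syncope |
| **10050093** | Altered state of consciousness |
| **10050093** | Consciousness fluctuating |
| 10058709 | Sopor |

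**Step 1: terms against codes.** There are 8 terms and 7 distinct codes, hence 8 − 7 = 1 duplicate, which is 10050093. In the SAP, the row printed between the two carries its own code, and the rows around them are intact, so neither redaction nor a broken table explains the repeat.

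**Step 2: does the SMQ list supply the missing code?** The convulsions SMQ list in the same section has 99 terms and 99 distinct codes. None of them is shared with the selective list. A term missed through the duplicate is therefore not picked up by the SMQ.

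**Step 3: does the appendix itself treat a code as belonging to one term?** In the cross-list repeats looked at, the code recurs with the same name:

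- Sopor (10058709) and Stupor (10042264) in sections 16.11.11 and 16.11.13
- Epileptic psychosis (10059232) in sections 16.11.8 and 16.11.13
- Hepatorenal failure (10019845) in sections 16.11.1 and 16.11.17

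The pair at 10050093 breaks that pattern.

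**Step 4: reach of the selection.**

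- By printed code: at most 7 of the 8 selected terms. Against the whole seizure grouping of 99 + 8 = 107 terms, that is at most 106 of 107.
- By preferred term name: all 8, and nothing is lost.

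**Step 5: rules that could repair the entry.**

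- The version-change rule in section 16.11 takes effect only if the MedDRA version changes. It would then correct the entry if codes are looked up again from the term names, but not if the look-up starts from the printed codes.
- The safety review team provision in section 8.2 decides which terms are included. It does not say that the printed codes are verified.

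**The case against.** The strongest reply is that the SAP never commits to filtering on the printed numbers. Appendix 11 allows coded values, AE data or both; every row prints the term name; and Table 3.71 is itself organised by preferred term. A programmer working from names loses nothing. The list is also provisional: the safety review team may replace it at reporting, and that later list cannot be seen here. Whether the slip reached any programmed term list is unknown.

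All of this stands. It makes the consequence conditional but leaves the printed inconsistency in place.

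Two stronger readings are tempting and are not supported:

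- A reader might infer that the plan as written will miss seizure-type events. That follows only if selection is by the printed code, and the document does not settle the method.
- A reader might infer that a MedDRA refresh cannot help because these terms are hand-selected and not part of an SMQ. Section 16.11 draws no such distinction. Its version-change rule follows a sentence covering all terms and codes listed below it, so it could correct this entry.

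It is also fair to say that no event would vanish from safety reporting. An adverse event of either term would still be counted under its own preferred term in Tables 3.4 and 3.5 and shown in Listing 12.

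**Conclusion.** The inconsistency is real and visible on the page: one code, two preferred terms, so at least one printed code in section 16.11.13 is wrong. The document does not show which one, or what the right code is.

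The possible consequence is an unnoticed omission from the seizure category in Tables 3.71 and 3.72. It rests on two assumptions: that selection uses the printed codes, and that neither the version-change rule nor the safety review team's list corrects the entry first. Neither assumption can be confirmed or excluded from the SAP.

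The size is minor. One of eight selected terms is in question on the reading that just one code is wrong. The SAP gives no event frequencies, so the number of affected events cannot be estimated. The displays are descriptive, and no primary, key secondary or other tested endpoint is involved. This is a correction worth making, not a threat to the trial's conclusions.

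**What to change.** 1. Check both codes against the MedDRA version used for reporting, and correct whichever is wrong in section 16.11.13.
2. Carry the correction into any term list programmed from Appendix 11.
3. Before database freeze, confirm for every hand-selected preferred term in Appendix 11 that name and code agree, and resolve any mismatch.

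The cost is a dictionary look-up, normally one corrected code, and a short consistency check. No analysis, endpoint or display changes.

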16.11.14. Weight Gain**HLT General nutritional disorders NEC (Selective)**

PT	PT Code
Abdominal fat apron	10077983
Overweight	10033307
Abnormal weight gain	10000188
Central obesity	10065941
Obesity	10029883

PTs (Select) - Physical examination procedures and organ system status

PT	PT Code
Weight abnormal	10056814
Weight increased	10047899
Waist circumference increased	10064863
Body mass index abnormal	10074506
Body mass index increased	10005897

PTs (Select) - General Signs and Symptoms

PT	PT Code
Fat tissue increased	10016251
Sarcopenic obesity	10083992

16.11.15. Rhabdomyolysis**Rhabdomyolysis/myopathy (SMQ)**

PT	PT Code
Muscle necrosis	10028320
Myoglobin blood increased	10028625
Myoglobin blood present	10059888
Myoglobin urine present	10028631
Myoglobinaemia	10058735
Myoglobinuria	10028629
Myopathy	10028641
Myopathy toxic	10028648
Necrotising myositis	10074769
Rhabdomyolysis	10039020
Thyrotoxic myopathy	10081524
Muscle infarction	10086278

PTs (Selective) - Muscle Disorders

PT	PT Code
Myalgia	10028411
Myositis	10028653

16.11.16. Pancreatitis**Acute pancreatitis (SMQ)**

PT	PT Code
Cullen's sign	10059029
Grey Turner's sign	10075426
Haemorrhagic necrotic pancreatitis	10076058
Immune-mediated pancreatitis	10083072
Ischaemic pancreatitis	10066127
Oedematous pancreatitis	10052400
Pancreatic abscess	10048984
Pancreatic cyst drainage	10082531
Pancreatic haemorrhage	10033625
Pancreatic phlegmon	10056975
Pancreatic pseudoaneurysm	10081762
Pancreatic pseudocyst	10033635
Pancreatic pseudocyst drainage	10033636
Pancreatic pseudocyst haemorrhage	10083813
Pancreatic pseudocyst rupture	10083811
Pancreatitis	10033645
Pancreatitis acute	10033647
Pancreatitis haemorrhagic	10033650
Pancreatitis necrotising	10033654
Pancreatitis relapsing	10033657
Pancreatorenal syndrome	10056277
Subacute pancreatitis	10084554
Walled-off pancreatic necrosis	10085347

16.11.17. Impact on Creatinine**Acute renal failure (SMQ)**

PT	PT Code
Acute kidney injury	10069339
Acute phosphate nephropathy	10069688
Anuria	10002847
Azotaemia	10003885
Continuous haemodiafiltration	10066338
Dialysis	10061105
Foetal renal impairment	10078987
Haemodialysis	10018875

PT	PT Code
Haemofiltration	10053090
Neonatal anuria	10049778
Nephropathy toxic	10029155
Oliguria	10030302
Peritoneal dialysis	10034660
Prerenal failure	10072370
Renal failure	10038435
Renal failure neonatal	10038447
Renal impairment	10062237
Renal impairment neonatal	10049776
Subacute kidney injury	10081980

Renal Failure and Impairment

PT	PT Code
Acute Kidney injury	10069339
Anuria	10002847
Atypical haemolytic uraemic syndrome	10079840
Cardiorenal syndrome	10068230
Chronic kidney disease	10064848
Crush syndrome	10050702
Diabetic end stage renal disease	10012660
End stage renal disease	10077512
Foetal renal impairment	10078987
Haemolytic uraemic syndrome	10018932
Hepatorenal failure	10019845
Hepatorenal syndrome	10019846
Nail-patella syndrome	10063431
Neonatal anuria	10049778
Oliguria	10030302
Pancreatorenal syndrome	10056277
Postoperative renal failure	10056675
Postrenal failure	10059345
Prerenal failure	10072370
Propofol infusion syndrome	10063181
Renal failure	10038435
Renal failure neonatal	10038447
Renal impairment	10062237
Renal impairment neonatal	10049776
Renal injury	10061481

PT	PT Code
Scleroderma renal crisis	10062553
Traumatic anuria	10044501

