Sleep Disorders	CAB+RPV	Clinical, Class, Regulatory Interest, More prevalent in HIV population
Injection Site Reactions (ISR) from Study Drug Injections [1]	CAB+RPV	Clinical
Seizures and Seizure-like Events	CAB	Clinical, Regulatory Interest
Weight Gain	CAB	Clinical, Class
Rhabdomyolysis	CAB	Clinical, Class
Pancreatitis	CAB	Clinical, Therapeutic Area, More prevalent in HIV population

Adverse Events of Special Interest	Drug(s) of Interest	Reason for Inclusion
Impact on Creatinine	CAB+RPV	Regulatory Interest, Therapeutic Area, More prevalent in HIV population
Safety in Pregnancy	CAB	Regulatory Interest, Class
NOTE: [1] A separate analysis will be performed for ISRs from study drug injections as described in Section 8.2.1		

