3.68.	Safety	SAF_T17	Summary of Substance and Illicit Drug Use (Maintenance Phase)	Q2M vs. BIK	M12
eC-SSRS					
3.69.	Safety	CSSRS1	By Phase Summary of Subjects with eC-SSRS Suicidal Ideation or Behaviour	207966/primary_15/T3.72 Q2M and BIK	M6, M12

Safety: Tables					
No.	Population	GSK Standard/ Example Shell	Title	Programming Notes	Deliverable [Priority]
AEs of Special Interest (AESI)					
3.70.	Safety	207966/primary_15/T3.73	By Phase Summary of Depression, Anxiety and Suicidal Ideation/Behaviour Adverse Events by System Organ Class, Preferred Term, Maximum DAIDS Toxicity Grade, and Prior History (Depression, Anxiety or Suicidal Ideation) at Screening	
3 Layers of section headers:
 
Phase: Oral Lead-In Period(Maintenance)/Maintenance
 
Treatment: Q2M, OLI(Q2M), D2I(Q2M), BIK
 
Subjects has: yes/no prior history of depression, yes/or prior history of anxiety, yes/or prior history of suicidal ideation
 
For Oral Lead-In period, only need to present the OLI(Q2M) groups
	M6, M12, EOS
3.71.	Safety	SAF_T16a and SAF_T16b	By Phase Summary of Adverse Events of Special Interest by AESI Category , System Organ Class and Preferred Term (Number of Subjects and Occurrence)	207966/primary_15/T3.75	M6, M12, EOS
3.72.	Safety	207966/primary_15/T3.109	By Phase Summary of Characteristics of Adverse Events of Special Interest	Add footnote: AESIs with at least 1 event are included in the summary.	M6, M12, EOS
3.73.	Safety	207966/primary_15/T3.111 and T3.112	By Phase Summary of Syncope and Presyncope Adverse Events		M6, M12, EOS
COVID-19 Assessments					
3.74.	Safety	207966 primary 15/Table 3.113	Summary of COVID-19 Adverse Events by System Organ Class, Preferred Term and Maximum Toxicity (Maintenance Phase)	Q2M and BIK only	M6, M12

Safety: Tables					
No.	Population	GSK Standard/ Example Shell	Title	Programming Notes	Deliverable [Priority]
3.75.	Safety	PAN1 / PAN1A	Summary of COVID-19 Assessments for Subjects with COVID-19 Adverse Events	Q2M and BIK only	M6, M12
3.76.	Safety	PAN3 / PAN3A	Summary of COVID-19 Symptoms for Subjects with COVID-19 Adverse Events	Q2M and BIK only	M6, M12
Additional Analysis					

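### The Impact on Creatinine AESI lists no creatinine, creatinine-clearance or GFR term, so AEs coded to such terms stay out of the AESI tables unless the list is changed at reporting

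*SAP*

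**What the plan says.** Section 8.2, Table 4, lists "Impact on Creatinine" as an AESI for CAB+RPV and gives as the reason for inclusion "Regulatory Interest, Therapeutic Area, More prevalent in HIV population". Section 8.2 refers to Appendix 11 for the terms.

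Appendix 11 sets a general rule in Section 16.11: "SMQs use narrow terms unless otherwise specified". Section 16.11.17 makes no exception to it. That section holds two term lists, headed "Acute renal failure (SMQ" and "Renal Failure and Impairment", and nothing else.

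The term lists feed Table 3.71, titled in part "By Phase Summary of Adverse Events of Special Interest by AESI Category", and Table 3.72, which describes the characteristics of these events. Both are planned for Month 6, Month 12 and end of study.

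**The concern.** A category named for creatinine would be expected to hold AEs reported as a raised creatinine, a reduced creatinine clearance or a reduced GFR. The listed terms are instead diagnoses, syndromes and procedures of renal failure, impairment or injury. An investigator's report coded to a creatinine investigation term falls outside the category, while terms such as nail-patella syndrome and propofol infusion syndrome fall inside it.

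What is at stake is how two descriptive safety tables are read. The programming note for Table 3.72 says that only AESIs with at least one event are shown. If creatinine AEs were reported but no event on the renal lists occurred, the category would be absent from that table. A reader could then take it that no creatinine AE had been reported.

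**Working it through.** The SAP states no figure to reproduce here. The check is a count of terms and a comparison with sibling sections of the same appendix.

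**Inputs.** Both PT lists in Section 16.11.17.

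**Count.**
- First list (the SMQ): 19 PTs.
- Second list: 27 PTs.
- In both: 10 PTs (acute kidney injury, anuria, foetal renal impairment, neonatal anuria, oliguria, prerenal failure, renal failure, renal failure neonatal, renal impairment, renal impairment neonatal).
- Distinct PTs: 19 + 27 − 10 = 36.

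**Search.** The 36 PTs were searched for text naming creatinine, clearance, glomerular, GFR or filtration rate. Result: 0 of 36.

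**Comparison within Appendix 11.** Other AESIs that concern a measured quantity do list a measurement term:
- Section 16.11.4 (QT) includes a PT for a prolonged QT interval on the electrocardiogram.
- Section 16.11.14 (Weight Gain) includes "Weight increased".
- Section 16.11.15 (Rhabdomyolysis) includes a PT for raised blood myoglobin.

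Six sections (hypersensitivity, rash, QT, seizures, weight gain, rhabdomyolysis) also add individually selected PTs to their main MedDRA grouping. Section 16.11.17 has no such addition, and the SAP gives no reason for leaving it out.

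**Where a creatinine AE would and would not appear, following the list as written.**

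| Display | Creatinine or GFR AE shown? |
|---|---|
| Tables 3.71, 3.72 (AESI) | No, under this category |
| Tables 3.4, 3.5 (all AEs by PT; by PT and maximum toxicity) | Yes |
| Tables 3.9, 3.10 (drug-related AEs by PT) | Yes, if drug-related |
| Table 3.17 (AEs leading to withdrawal or discontinuation, by PT) | Yes, if it led to either |
| Tables 3.29, 3.30, 3.77, 3.78 (chemistry changes and toxicities) | Laboratory values only, not reported AEs |

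**The case against.** Four points can be made for the plan.

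*The list is provisional.* Section 8.2 says that the terms will follow the safety review team's agreements at reporting, and Section 16.11 lets events be added after a blinded review before database freeze. This stands in part: the exclusion is not final. But both clauses are general, neither names a creatinine term, and neither obliges anyone to add one. Section 2.3 describes the study as open-label, so naming an evident term in advance is cleaner than choosing it after AE data have been looked at.

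*Nothing is lost from the report.* This stands. A reader might infer that raised-creatinine AEs, their relation to study drug or the withdrawals they cause go unreported. The general AE tables set out above show otherwise, and laboratory creatinine and GFR have their own displays.

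*The category may be meant for clinical renal events.* Table 4 gives only broad reasons for inclusion, so a purpose of capturing mild creatinine rises cannot be read out of the document. If clinical renal events are what is meant, the list may be right and the name wrong. That changes the remedy, not the existence of the mismatch.

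*The list is wider than organ failure.* This also stands. It includes renal impairment, renal injury, azotaemia, oliguria and toxic nephropathy, so it would be wrong to say that it captures organ failure alone. None of these terms is a creatinine or GFR term.

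**Conclusion.** The name and the term list of this AESI do not match: 0 of its 36 distinct PTs is a creatinine, creatinine-clearance or GFR term. AEs coded to such terms would be absent from the category in Tables 3.71 and 3.72, in both arms alike. This assumes that the list is used as written and not amended under the optional clauses.

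The point is small. It touches one descriptive safety grouping with no test or decision rule attached, and no efficacy conclusion depends on it. The number of participants affected cannot be given, because the SAP states no expected rate of creatinine AEs. It would also go too far to say that widening the scope of the SMQ would cure the gap: the SAP prints only the terms it uses and does not show what a wider scope would add.

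**What to change.** Add a list of selected PTs to Section 16.11.17, in the form already used in Sections 16.11.2 to 16.11.4 and 16.11.13 to 16.11.15. It should hold the investigation terms for creatinine, creatinine clearance and GFR, with names and codes from the MedDRA version in force. Show these terms in Tables 3.71 and 3.72 on a line separate from the renal failure and impairment terms, so that the more serious events stay visible.

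If the team intends only renal failure, impairment and injury events, keep the lists and rename the AESI in Table 4 and Section 16.11.17 to say so.

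The cost is a few lines of SAP text and, with the first option, a slightly longer term list and a possibly higher count in the category.
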